Interventions for Unemployed Hazardous Drinkers

NCT02559609

Protocol V. 6/21

PROTOCOL: Interventions for unemployed hazardous drinkers

PRINCIPAL INVESTIGATORS: [name], and [name]

Despite recent improvements in the US economy, unemployment remains a significant concern, and estimates indicate that one-third of unemployed persons drink at hazardous levels, adversely impacting their health and abilities to find jobs. Reinforcement interventions are highly efficacious in reducing substance use, and they can be applied to increase job-seeking activities as well. In partnership with CT United Labor Agency, this project is designed to reduce hazardous drinking and enhance active participation in job-seeking activities among those with job loss. It will evaluate the independent and combined effects of reinforcing negative breathalyzer samples and job-seeking activities to ascertain the simplest and most cost-effective approach to improving outcomes in this population. Unemployed individuals with hazardous drinking ($N = 280$) will be randomly assigned to one of four conditions using a 2×2 design: standard care, standard care with reinforcement for submitting negative breathalyzer samples, standard care with reinforcement for job-seeking activities, or standard care plus reinforcement for both negative breathalyzer samples and job-seeking activities. Participants in all conditions will receive usual services part of CT United Labor Agency, along with a novel remote breath alcohol monitoring procedure. The study interventions will be in effect for three months, and participants will be followed for one year. Alcohol and other drug use, employment, psychiatric symptoms, and global measures of health will be assessed throughout treatment and follow-up. Reinforcing negative breathalyzer samples is expected to significantly reduce drinking, and reinforcing job-seeking activities is expected to increase re-employment rates and reduce time until job attainment. Reinforcing both negative breathalyzer samples and job-seeking activities is hypothesized to improve outcomes along both domains. The reinforcement interventions may also decrease psychiatric distress and slow progression of physical decline, common among the unemployed. If efficacious and cost-effective, results from this study may stimulate adoption of reinforcement interventions in the context of unemployment services. Reducing the adverse consequences of hazardous drinking and improving job re-entry may have pronounced benefits in a highly vulnerable segment of the US population.

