Additionally, this study will estimate the costs and cost-effectiveness of the reinforcement interventions relative to usual care. If they increase the proportion of individuals who transition to re-employment and reduce time to job attainment, reinforcement interventions may be cost-effective and ultimately integrated in the context of unemployment services. Importantly, reinforcement interventions are now being applied nationwide in the context of substance abuse treatment services ([name] et al., in press b) as well as in other health care arenas (National Business Group on Health, 2013). These dissemination experiences bode well for their ultimate adoption in the context of unemployment services, if benefits are found in this study.

Significance

The unemployment rate in the US remains 7.7% (Bureau of Labor Statistics, 2013), and this rate disguises a larger change in employment patterns, in which precarious or impermanent jobs, that encompass a triad of contingent duration of employment, absence of benefits, and reduced compensation, are increasing (Kalleberg et al., 2000). In part because of this trend, our nation is experiencing the highest poverty level since the early 1980s (Danziger et al., 2012), with a 45% increase in food stamp program enrollment between 2009 and 2012 (Tavernise, 2012). Health disparity groups, including racial/ethnic minorities and those with substance use problems, are most impacted by job loss and unemployment.

Recent data from the National Survey on Drug Use and Health (SAMHSA, 2011) indicate that 33.2% of the unemployed binge drink, and 14.8% have an alcohol use disorder, nearly double the rate of employed persons. The loss of a job, especially involuntary job loss, results in substantial financial, family, and personal stress, along with an increase in unstructured time, all of which can impact alcohol use (Forcier, 1988). Most cross-sectional studies have found greater frequency of hazardous drinking in unemployed versus employed samples (Bolton & Rodriguez, 2009; Dooley & Praise, 1998; Khalt et al., 2004; Mulia, et al., 2013). Longitudinal studies likewise demonstrate that loss of employment can result in greater alcohol consumption and problems (Catalano et al., 1993; Claussen, 1999; Davalos et al., 2012; Mossakowski, 2008; Popovici & French, 2013; Thomas et al., 2005), particularly among men (Virtanen et al., 2008; Deb et al., 2011) and individuals with lower educational attainment (Deb et al.,

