In a randomized clinical trial, we (Drebog et al., 2007) evaluated the efficacy of a reinforcement intervention in 100 veterans with significant psychiatric problems and drug dependence who were participating in a vocational rehabilitation program. Patients were randomly assigned to usual care vocational rehabilitation services alone or with reinforcement for 16 weeks. The reinforcement intervention offered up to \$1,170 for drug and alcohol negative samples and completing tasks related to job search and maintenance. Relative to those in the vocational rehabilitation only group, those in the reinforcement intervention achieved more abstinence, completed more intensive job searches, and transitioned to competitive employment faster and at higher rates, with 50% vs 28% ($p<.01$) obtaining a job during the study period. These results suggest that adding reinforcement to vocational training programs holds potential to substantially improve outcomes along both employment and substance use domains. That study reinforced both substance negative samples and job-related activities. The present study will disentangle effects of the two behavioral targets as well as ascertain whether either is sufficient, or both are necessary, to improve outcomes, a question of theoretical and practical importance for bringing these interventions to community-based employment agencies.

We also have experience estimating cost-effectiveness. In prior studies, we demonstrated that our prize reinforcement system is not only efficacious but also cost-effective in improving outcomes (Olmstead et al. 2007abc, 2009; Sindelar et al., 2007ab). These data are particularly compelling in the context of unemployment agencies, which may realize overall cost savings by transitioning displaced workers more quickly into employment. Thus, we will estimate costs of interventions and their administration, as well as benefits from individual and societal perspectives. These data will help inform decisions about for whom and under what circumstances funders or society may be willing to pay for increased costs of these interventions.

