participants will receive standard employment agency services, including access to workshops, trainings, computers, and a case manager. Study participants will also meet with RAs weekly for 12 weeks. During brief ~20 min meetings, RAs will assist participants in selecting 3 specific job-related activities they can accomplish in the upcoming week. A contract will detail activities, with the purpose of breaking goals into more readily achievable components. Examples include: attending a job club, meeting with a case manager or vocational training specialist, making a chart of potential employers and persons within each hiring agency to call about jobs, completing an in-person or online job training sessions, listing questions to ask at an interview, attending a mock job interview, coming to a clinic appointment dressed in an appropriate manner for a job interview, volunteering, completing a resume, filling out a job application, attending a job interview, writing a thank you note to an interviewer, etc. In initial weeks of the study and for low functioning participants throughout, activities may be simple such as handwriting a resume one week, incorporating improvements the next, then typing it, etc. A higher functioning patient may tailor resumes to specific jobs, attend an intensive workshop, and send in 5 job applications in a week. Once a job is obtained, activities may include going to work on time or enrolling in additional workshops to further skills. RAs will review and provide positive verbal feedback (albeit no tangible reinforcer) for each activity completed to equate for attention across conditions and isolate potential benefits of the activity reinforcement conditions explicitly to the tangible reinforcers. At brief weekly meetings, RAs will also obtain TLFB self-reports of drinking and drug use and provide compensation for BrAC tests, as outlined below.

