The design includes four treatment groups, allowing for examination of three main contrasts. Aim #1 is to evaluate whether reinforcing negative BrACs reduces drinking. Contrast weights of +1 will be assigned to Groups B and D and weights of -1 to Groups A and C to evaluate differences in LDNS and % negative BrACs in those assigned to interventions reinforcing negative BrACs vs those not. Aim #2 is to assess if reinforcing job-related activities reduces time to job attainment and increases % days working. Contrast weights of +1 will be assigned to Groups C and D and -1 to Groups A and B. Aim #3 is to examine if reinforcing both negative BrACs and job activities produces synergistic effects in terms of primary drinking and employment outcomes. To test this hypothesis, we will assign contrast weights of +2 to Group D, +1 to Groups B and C and -3 to Group A.

Power analyses. Our studies reinforcing drug abstinence find Cohen's d effect sizes of 0.5 to ≥ 1.0 for substance use outcomes ([name] et al., 2000, 2004, 2005abc, 2006b, 2007a, 2010b, 2011a, 2012abc), and our pilot trial using cell phone recorded BrACs yielded an effect size of $d=0.52$ for LDNS and $d=0.62$ for % negative BrACs ([name] & [name], 2013). Our study reinforcing job activities and abstinence (Drebing et al., 2007) had an effect size of 0.47 in terms of increasing job acquisition and 0.49 for abstinence. We conservatively powered this study to detect the smallest of these effect sizes. Using a Type I error rate of $\alpha=.05$, a Type II error rate of $\beta=.20$, and power=0.80 (Cohen, 1988), 62 participants are needed to detect

an effect size of $d=0.47$ between conditions reinforcing a target behavior and conditions not reinforcing that behavior.

We expect a smaller, but still clinically meaningful, effect size of $f=.22$ when comparing across reinforcer conditions. With power 0.80, 64 participants/group can detect $f=.22$ using the 3-group contrast in Aim 3 (Cohen, 1988). To accommodate for missing data, we will randomize 280 participants in total (70/group).

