With 70 participants/group in a 2x2 design, we will be overpowered to detect main effects of reinforcing negative BrACs on alcohol outcomes, and main effects of reinforcing job-related activities on employment outcomes. Nevertheless, this sample size provides power to ascertain if the combined reinforcement intervention is most effective. It also allows detection of a small to medium effect size in determining if reinforcing one behavior can improve both alcohol and employment outcomes (e.g., Group B > A, and Group C > A) to isolate the simplest efficacious reinforcement approach. Moreover, it permits evaluation of secondary outcomes and exploratory analyses of moderators and mediation effects.

Secondary aims are to evaluate the impact of interventions on other drug use, and mental and physical health indices. These are continuous measures, with missing data likely. If no systematic differences in missing data are noted, hierarchical linear models (HLM; Gibbons et al., 1993) using MIXREG (Hedeker, 1993) will analyze differences between groups over time. These analyses have advantages over repeated measures ANOVA as they estimate missing data via model parameter estimates and use real time, rather than scheduled time, of assessments. The same contrasts outlined above will be used to evaluate the aims. Analyses will be conducted for both short-term (e.g., BL to M3, with up to 3 data points/participant: BL,M1,M3) and long-term effects (BL through M12, with up to 6 data points: BL,M1,3,6,9,12). Models will include factors for group (using contrasts above), time, and interaction of group by time. Analyses will ascertain whether the interventions impact areas of functioning beyond alcohol use and employment indices. For example, reinforcement interventions can reduce psychiatric symptoms and improve quality of life ([name] et al., 2007b, in press c).

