- i. Random group assignment is used, and participants have about a 75% chance (210 of 280) of being assigned to a reinforcement group (70 are in the standard care condition; see power analyses). Participants may voluntarily end study participation if they are dissatisfied with their assignment.
- ii. The interviews and sample collections are brief, participants may skip questions or take a break if uncomfortable, and the particular sample assays chosen are intended to minimize discomfort.
- iii. All participants will be informed (in the informed consent form, at clinic visits, and via phone and text reminders) that they will be expected to submit breathalyzer samples within 1 hour of requests. Missing more than 50% of BrAC tests in a week will result in cell phone discontinuation (or cessation of \$35/month payment for cell phone service if using one's own study-compatible phone). The consent form will state explicitly that all study participants will be asked to submit between 7 and 21 samples per week in weeks 1-12 to maintain cellular service (or the \$35 payment), and that failure to submit

at least 50% of requested samples in a week may disqualify them from further participation in the breathalyzer component of the study. Participants will be informed of how to reinstate cellular service (or their \$35/month cell phone payments) in the consent form (i.e., they need to submit an unprompted breathalyzer test). If cellular service is discontinued, they will also be contacted to inform them of the process about how to restore it (i.e., submit a test). While cellular service will be reinstated once during the course of the 12-week study, participants will no longer be eligible for cellular service (or the \$35/month payment of their cell plan) and the BrAC payments for sample submission if they fail to submit 50% of samples for two weeks during the study period.

Participants will be informed that if they get a job in which they work evenings and/or weekends, their BrAC testing schedule can be altered so as not to interfere with their work hours. Participants who successfully obtain jobs during the course of the 12-week intervention period will be required to show proof of their working hours (e.g., paystubs, work schedules) if they are requesting a change from the typical BrAC prompt schedule, designed to request samples primarily during evening and weekend times.

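### No randomised arm is usual care: Groups A and B also get 12 weeks of job-activity contracting, so cost-effectiveness against usual care cannot be estimated, and transferring d = 0.47 to Aim 2 is an unargued assumption

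*Combined protocol and SAP*

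**What the plan says.** **Labels.** The opening summary lists standard care as one of the four conditions and states: "Participants in all conditions will receive usual services part of CT United Labor Agency, along with a novel remote breath alcohol monitoring procedure". It does not mention contracting. Specific aims says "this study will estimate the costs and cost-effectiveness of the reinforcement interventions relative to usual care". Net benefits, under Economic Evaluation, sets the reinforcement conditions against standard care. Human Subjects 2.b says "70 are in the standard care condition".

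**What is delivered.** The Group A heading in Methods names three components: standard services, job-activity contracting and alcohol monitoring. The text gives weekly research-assistant meetings of about 20 minutes for 12 weeks and a contract for three specific job activities per week. It adds that "RAs will review and provide positive verbal feedback (albeit no tangible reinforcer) for each activity completed", and gives the reason: to equalise attention across conditions and isolate the tangible reinforcer. The Group B text gives that group the same weekly selections. The Group C text confirms that all three groups contract.

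**Aim 2.** Specific aims compares participants reinforced for job activities with those not reinforced. Data Analysis tests this as C and D (+1) against A and B (-1).

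**Sizing.** Power analyses reports that the earlier veterans trial "had an effect size of 0.47 in terms of increasing job acquisition", and sizes on that effect as the smallest available. Preliminary studies describes that trial: "Patients were randomly assigned to usual care vocational rehabilitation services alone or with reinforcement for 16 weeks". It reinforced both substance-negative samples and job tasks. Power analyses concludes that "we will be overpowered to detect main effects of reinforcing negative BrACs on alcohol outcomes, and main effects of reinforcing job-related activities on employment outcomes".

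**Costs.** Economic Evaluation item a counts the cost of setting and verifying job activities in Groups C and D only.

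**The concern.** Contracting with feedback acts on job-search effort, which the Significance section links to re-employment. Giving it to every arm isolates the prizes, but it changes what the comparison can answer in two ways.

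- **Economics.** A result described as relative to usual care needs an arm without contracting. None exists. If activity setting is costed as incremental in C and D while its benefit is also present in A and B, costs and effects belong to different comparisons.
- **Power for employment.** The 0.47 was observed against usual services alone, with two behaviours reinforced. Aim 2 compares prizes plus contracting with contracting, and half of its reinforced side (Group C) is reinforced for job activities only. The plan gives no reason why 0.47 should carry over, yet calls the study overpowered for this contrast.

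At stake are the interpretation of the cost-effectiveness ratio and how a null Aim 2 result would be read.

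**Working it through.** **1. Comparator by place in the document**

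| Place | Comparator described as |
|---|---|
| Opening summary; Human Subjects 2.b | standard care |
| Specific aims (economic aim) | usual care |
| Net benefits | standard care |
| Specific aims (Aim 2) | not reinforced for job activities |
| Group A heading and text; Group B text | services + contracting + paid monitoring |

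The last two rows are compatible with each other. The first three describe an arm that is not randomised.

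**2. Cost-effectiveness ratio, C v A**

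Let c_k and e_k be the cost and effect of contracting over usual services. Let c_p and e_p be the cost and effect of verification and prizes added to contracting.

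- As item a is written: (c_k + c_p) / e_p.
- Consistent ratio for prizes added to contracting: c_p / e_p.
- Consistent ratio against usual care: (c_k + c_p) / (e_k + e_p). Here e_k cannot be estimated, because every arm contracts.

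If e_p > 0 and e_k is not negative, the ratio as written is at least as large as either consistent one, so it leans against job reinforcement. It equals the usual-care ratio only if e_k = 0. The documents give no staff unit cost, so no dollar figure is possible. Meeting time is about 12 x 20 = 240 minutes per participant, and only part of that is contracting.

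**3. The plan's own sizing figure**

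Inputs from Power analyses: d = 0.47, alpha .05, power .80. Sidedness is not stated; two-sided is assumed.

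n per side = 2 x ((1.960 + 0.842) / 0.47)^2 = 71.1, so 72 (one-sided: 56). The stated 62 does not reproduce; read as 62 per side it gives 74% power two-sided. This is a separate matter and does not drive the point here.

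The 0.47 itself agrees with the source trial's 50% v 28% employed: Cohen's h = 2 asin(sqrt .50) - 2 asin(sqrt .28) = 0.456.

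**4. Is the study overpowered if 0.47 transfers?**

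Power = Phi(d x sqrt(n/2) - 1.960).

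- 140 v 140 (70 per group): 0.47 x 8.367 - 1.960 = 1.972, power 97.6%.
- 128 v 128 (64 per group, before the missing-data allowance): 0.47 x 8 - 1.960 = 1.800, power 96.4%.

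So the claim follows if the effect carries over intact.

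**5. How much can be lost?**

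Detectable d at 80% power = 2.802 / sqrt(n/2): 0.335 at 140 v 140 and 0.350 at 128 v 128 (0.336 and 0.352 by the t-test). That is 71% and 75% of 0.47. The documents give no figure for the share retained, so a range is shown:

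| Share of 0.47 retained | d | 140 v 140 | 128 v 128 |
|---|---|---|---|
| 100% | 0.470 | 97.6% | 96.4% |
| 90% | 0.423 | 94.3% | 92.3% |
| 80% | 0.376 | 88.2% | 85.3% |
| 70% | 0.329 | 78.6% | 74.9% |
| 60% | 0.282 | 65.5% | 61.6% |
| 50% | 0.235 | 50.2% | 46.8% |

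**6. Time to job attainment**

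Hold the reinforced arm at 50% by week 16 and let contracting raise the control rate above 28%. Under exponential times, HR = ln(.50) / ln(1 - pC), and power = Phi(ln(HR) x sqrt(events)/2 - 1.960).

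| Control rate at 16 weeks | HR | Events, power at 16 weeks | Events, power at 52 weeks |
|---|---|---|---|
| 28% | 2.11 | 109, 97% | 217, >99% |
| 33.5% | 1.70 | 117, 82% | 228, 98% |
| 39% | 1.40 | 125, 47% | 237, 74% |

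The 52-week column assumes proportional hazards, no dropout and a Cox analysis over the full year.

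**The case against.** The strongest reply is that contracting in the control arms is disclosed and deliberate. The Group A heading names it, the text gives the attention-control reason, and Aim 2 is worded as reinforced against not reinforced. All of that stands: Aim 2 does not claim a usual-care comparator, and the contrast is valid for what it estimates.

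An economist might add that a real agency would not contract with clients, so charging contracting only to C and D reflects the cost of adoption. That is defensible on the cost side, but it needs an effect against usual services, which no arm supplies. Item a does explain why unreinforced breath monitoring is left out of Groups A and C, as data collection. It gives no such reason for activity setting in A and B.

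Three stronger readings are tempting, and the documents do not support them.

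- **That the overpowered claim is wrong.** No document gives the effect of contracting with feedback, and there is room to lose 25% to 29% of 0.47 before power drops below 80%.
- **That a control job rate of 33.5% brings power to 80%, and 39% to 46%.** Those figures use a 16-week binary job rate, which is not a primary outcome (those for employment are percent days worked and time to job attainment). They also use a 50% rate from an arm reinforced for both behaviours. The 52-week column above is far more favourable.
- **That Future directions would read a null result as failure against standard care.** That section does not name a comparator.

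Whether the veterans trial's control arm included any contracting cannot be settled from the short description given.

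**Conclusion.** The point holds in a limited form. No randomised arm is usual care, four places say or imply otherwise, and the trial cannot estimate effect or cost-effectiveness relative to usual care. The economic plan carries an internal inconsistency: activity setting is delivered in all four arms but costed in two, so the ratio mixes the cost of contracting plus prizes with the effect of prizes alone. The direction is against job reinforcement if prizes help and contracting does no harm; the size cannot be computed from the documents.

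For Aim 2, carrying 0.47 over from a different comparator and a dual-target intervention is an assumption the plan does not argue. It is not a demonstrated error: power is about 98% if 0.47 applies and stays at 80% or more while at least 71% of it (140 v 140) or 75% (128 v 128) is retained. These figures assume a two-sided 5% test on a continuous outcome. The total sample size is not called into question here, since 64 per group was set by Aim 3.

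**What to change.** 1. In the opening summary, Specific aims (economic aim), Net benefits and Human Subjects 2.b, name the comparator as the Group A heading already does: services plus contracting plus monitoring.
2. State the economic conclusions, and those on job reinforcement in Future directions, as the effect of prizes added to that package.
3. In Economic Evaluation item a, treat the cost of activity setting the same way in all arms, so that only verification and prize costs are incremental for job reinforcement.
4. In Power analyses, replace the overpowered statement for employment with the detectable effect at 80% power: d about 0.34 at 140 v 140 and 0.35 at 128 v 128, or 71% to 75% of 0.47. Note that 0.47 came from a different comparator and an intervention on two targets. Do not substitute a table built on 16-week job rates.

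Cost: wording, one costing rule and one recalculated power sentence. The claim becomes narrower and the power statement less favourable. Arms, visits and sample size stay as they are.

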During the 12 weeks, if no recordings are made within the hour for 3 consecutive 1-hr prompt windows, RAs will phone participants to inquire about any problems experienced and remind them of the compensation for complying and penalties for non-compliance. Further, if >40% of tests are missed in a week, RAs will phone to remind them that the service will be disconnected (or the \$35 monthly phone service fee forfeited) if they do not submit at least 50% of requested BrAC tests each week. To re-instate service, participants must submit an unprompted breathalyzer test. Phone service will only be reinstated once during weeks 1-12, such that missing >50% of prompts for two weeks during the three month intervention period will result in discontinuation of cell service (or cell phone payments) and BrAC payments throughout the remainder of intervention phase. Individuals who fail to participate in BrAC monitoring will be encouraged to continue with other aspects of study (and non-study) treatment and follow-ups, but they can also decline (see Human Subjects).

Two weeks before the 12-month follow-up, participants will be invited back for a brief re-training on remote BrAC procedures. They will be asked to complete BrACs when prompted for 14 days using similar procedures outlined above (and further detailed below).

Randomization: After completing BL and training, participants will be randomly assigned to a treatment group. A computerized urn randomization program (Stout et al., 1994) will balance participants on AUDIT scores (< or \geq 12), time since last worked for pay (< or \geq 12 months), and gender, variables likely to impact outcomes. Prior to randomizing participants, up to 10 pilot participants will complete a pilot study consent form and study procedures described for Group D below, through month 3 follow-up, for the purpose of monitoring staff on study procedures prior to the randomized trial. Pilot participants may not meet all inclusion or exclusion criteria, with the exception of those relating to safety and loss of benefits.

Group A (n=70; Standard services plus job activity contracting and alcohol monitoring)

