Timeline: Months 1-3 will be used for training, start-up efforts and pilots. We expect to randomize about 7-8 participants into the study each month in months 4-42. This rate of recruitment is feasible because over 500 unique clients receive services each month at CTULA, with an estimated 15-20% meeting all inclusion criteria (and $<15\%$ are expected to meet exclusion criteria). Given the number of clients served throughout this agency, we plan to limit recruitment to one or two of the employment agency sites, but can expand to other sites if needed. Recruiting more quickly would necessitate more study staff due to the number of intervention visits, and this rate is consistent with our substance abuse treatment studies. With this enrollment rate, all intervention should be completed by month 47 and final follow-ups by month 55, leaving 5 months for analyses and report writing.

Data Analysis: An important issue preceding analyses is to identify baseline differences between groups despite random assignment. Group differences that may relate to outcomes (e.g., psychiatric diagnoses, occupational or medical status, drinking severity, services received) will be used as covariates or fixed factors in analyses. All randomized participants will be included using intent-to-treat analyses. Four primary outcomes are determined a priori: longest duration of negative samples (LDNS), % negative BrACs, % days worked for pay, and time to job attainment. The first three are continuous variables that can be transformed if needed. Drinking outcomes rely primarily on objective indices (BrACs), with subjective reports supplementing objective indices, such that one can be considered drinking if either index is positive. For LDNS, missing BrACs will be considered to break a string of negative samples. For % negative BrACs and % days working, missing data will be considered missing (not impacting the denominator) in one analysis, and positive/not working in another to consider the range of possibilities. ANOVAs (or ANCOVAs) will be conducted for drinking data and % days employed, evaluating both short-term (BL to month 3) and longer-term (throughout follow-up) efficacy. Time to job attainment will be evaluated with Cox survivor analyses, including covariates if needed.

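### Primary-model covariates are to be picked from observed baseline differences, and the three urn factors are not committed to any primary model: a small, nearly free gain in precision and prespecification is left unused

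*Combined protocol and SAP*

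**What the plan says.** The Data Analysis part of Methods opens with "An important issue preceding analyses is to identify baseline differences between groups despite random assignment". It then states the rule: "Group differences that may relate to outcomes (e.g., psychiatric diagnoses, occupational or medical status, drinking severity, services received) will be used as covariates". The sentence goes on to allow such variables as fixed factors too. The named variables are examples, not a closed list, and neither a significance level nor a size of difference is given as the trigger.

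There are four primary outcomes: longest run of negative samples, percentage of negative breath tests, percentage of days worked, and time to a job. For the first three, "ANOVAs (or ANCOVAs) will be conducted for drinking data and % days employed". For the fourth, "Time to job attainment will be evaluated with Cox survivor analyses, including covariates if needed".

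Under Randomization, a computerized urn "will balance participants on AUDIT scores" (cut at 12), on time since last paid work (cut at 12 months), "and gender, variables likely to impact outcomes". The urn's parameters are not given.

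The contrast paragraph, which begins "The design includes four treatment groups, allowing for examination of three main contrasts", lists group weights only. The mixed models for secondary outcomes contain group, time and their interaction. AUDIT, duration of unemployment and gender do appear beside treatment condition in the later regression paragraph, but there the aim is to find which patient factors predict outcome.

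**The concern.** The plan identifies three variables as prognostic and balances allocation on them. It then chooses covariates by a rule, observed imbalance, that balancing makes less likely to select those same variables. Whether a covariate happens to differ between arms says little about how much outcome variance it explains, so the rule is a poor way to recover precision.

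Three things are at stake:

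- **Precision.** Known prognostic information is left out of the primary tests.
- **Standard errors.** If allocation is balanced on prognostic factors that the model omits, the model's standard error does not credit that balance and tends to be too large.
- **Prespecification.** With an open list, no threshold, and Cox covariates entered only as needed, the primary model is not fixed before the data are seen.

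**Working it through.** **Inputs from the documents.** N = 280, 70 per group; α = 0.05 (two-sided assumed, since sidedness is not stated); d = 0.47 for conditions that reinforce a behaviour against those that do not. Aims 1 and 2 each compare two groups with the other two, so 140 vs 140.

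**Assumed.** R² of the three urn factors together: 0.05-0.10. Urn parameters. d = 0.47 for the single-group comparisons (B vs A, C vs A), for which the plan gives no effect size.

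**The plan's own figure.** The power section says 62 participants are needed for d = 0.47 at 80% power. With noncentral t, two-sided, 62 per arm gives 0.74 and about 73 per arm are needed; 62 per group (124 vs 124) gives 0.96. The figure does not reproduce on either reading. That is a separate matter and does not affect what follows.

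**Power with and without adjustment.** The noncentrality is d/√(1−R²) × √(n/2), with n per side. Residual degrees of freedom are 276 (140 vs 140) or 138 (70 vs 70), less 3 when adjusted.

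| Comparison | Unadjusted | R² = 0.05 | R² = 0.10 |
|---|---|---|---|
| 140 vs 140, noncentrality | 3.932 | 4.034 | 4.145 |
| 140 vs 140, power | 0.975 | 0.980 | 0.985 |
| 70 vs 70, noncentrality | 2.781 | 2.853 | 2.931 |
| 70 vs 70, power | 0.788 | 0.809 | 0.829 |

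The gain is 0.5-1 points for Aims 1 and 2, and 2-4 points for 70 vs 70.

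**Aim 3.** No gain is quoted. The printed weights are +2 (D), +1 (B), +1 (C) and −3 (A), and 2 + 1 + 1 − 3 = +1. Weights that do not sum to zero do not define a contrast between groups. The sample-size sentence, "64 participants/group can detect $f=.22$ using the 3-group contrast in Aim 3", describes a different test from the four-group weighting in the analysis text.

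**Would the screen bring the urn factors in?** If three independent factors were each tested at p < 0.05 without balancing, at least one would be flagged in 1 − 0.95³ = 14% of trials. Under simulated urns at N = 280, any of the dichotomized factors was flagged in about 3-5%. When the continuous forms were screened as well, it was about 8%. In the simulation that included both forms (4,000 trials per setting), 70 vs 70 power at R² = 0.05/0.10 was 0.788/0.796 unadjusted, 0.788/0.799 with the screen, and 0.801/0.831 with the three factors fixed. The screen recovers almost none of the gain.

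**Bias and standard errors, linear contrasts.** Simulated mean error was below 0.005 SD, so there is no bias. Under exact balance the unadjusted standard error is too large by 1/√(1−R²), which is 1.026 at R² = 0.05 and 1.054 at 0.10. The true α is then 2[1 − Φ(1.96/√(1−R²))] = 0.044 and 0.039. A real urn balances only approximately: the excess was about 0-6% across the simulated urns.

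**Cox model.** With a conditional hazard ratio of 1.6 and three omitted binary factors of log hazard ratio 0.3, 0.6 or 0.9 each, the unadjusted hazard ratio was 1.58, 1.54 or 1.44, against 1.61, 1.64 or 1.59 adjusted (300 trials per setting). The change in power depends on what is held fixed:

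- In that setting, omission moved power from 0.92/0.93/0.90 to 0.91/0.85/0.72.
- With marginal job rates instead held at the 28% vs 50% of the veterans' trial in Preliminary studies, 140 vs 140, adjustment moved power from 0.972/0.972/0.973 to 0.970/0.977/0.985.

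No single Cox gain should be quoted.

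**Type I error.** With a fixed p < 0.05 screen, simulated error was 0.042-0.049. When the smallest p-value was taken among unadjusted, screened and single-covariate models with 4 to 8 candidates, it was 0.084-0.098.

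**The case against.** The strongest reply is that this is a preference, not an error. The three stated contrasts are the plan's main tests. For the first two, unadjusted power is already 0.975, and the plan itself says it has more power than it needs for those main effects. The larger gains fall on B vs A and C vs A, which are not among the three contrasts and for which d = 0.47 is borrowed. All of this stands, and it is why the point is minor.

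It can also be said that the rule may admit the urn factors after all. Drinking severity and occupational status are named as candidates, the urn works only on cut-points so continuous AUDIT or duration may still differ, and covariates entered in the Cox model as needed are not limited to imbalanced ones. That is fair: exclusion is likely, not certain. But nothing commits these variables to a primary model.

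A reader might infer that the primary analysis is biased or invalid. The linear contrasts are unbiased, and the error in their standard errors is small and conservative. The unadjusted hazard ratio estimates a marginal quantity, which is not in itself wrong.

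A reader might also infer that the plan inflates type I error. A fixed-threshold screen does not. The 0.084-0.098 describes free choice of the most favourable model, which the plan does not propose but also does not rule out. The reassurance under a screen likewise rests on a p < 0.05 threshold that the plan never states.

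**Conclusion.** The point holds as a minor one, best labelled a free improvement. The plan chooses primary-model covariates from observed differences and does not commit its own balancing factors to any primary model. The cost is some lost precision, slightly conservative standard errors for the linear contrasts, a hazard ratio whose meaning depends on which covariates enter, and a primary model left open to discretion.

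No conclusion on Aims 1 or 2 is likely to turn on the power gain alone. The sizes rest on the assumed R² and, for the single-group comparisons, on the assumed effect: at d = 0.35 the 70 vs 70 power would go from 0.54 to 0.56-0.58. The screening and standard-error results also rest on assumed urn settings. The lack of prespecification needs no assumption, since it can be read directly from the text.

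**What to change.** Before any outcome data are examined by group:

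1. Name AUDIT, time since last paid work and gender as fixed covariates in all four primary models (three ANCOVAs and the Cox model).
2. State their form in advance: dichotomized as in the urn, or continuous with any transformation named.
3. Move imbalance-driven adjustment to a labelled sensitivity analysis.
4. Label the adjusted hazard ratio as a conditional estimate.

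The cost is wording in the analysis plan and 3 degrees of freedom, from 276 to 273 (138 to 135 for a 70 vs 70 comparison). No new data are needed, because the urn requires all three values before a participant is allocated.
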